8.8.3 Concomitant Medications

A secondary measure of safety will be the reporting of concomitant medications. All concomitant medications collected from Screening to Study Termination will be categorized as follows:

- Pretreatment medications are defined as medications taken prior to and after signing informed consent and those taken during the Preparatory Period prior to the first Experimental Session. A stop date is expected prior to the first Experimental Session for any medications requiring a change in dose, a skipped dose, or tapering.
- Treatment Period concomitant medications are defined as those taken or continued during the Treatment Period from the first Experimental Session to the last Integrative Session. A stop date is expected prior to the each Experimental Session for any medications requiring a change in dose, a skipped dose, or tapering.
- Concomitant medications with a start date of the day of and two days after IP administration

- Follow-up Period concomitant medications are defined as those taken or continued during the Follow-up Period after the last Integrative Session through Termination
- Any concomitant medications that are tapered
- Any concomitant medications that are taken to treat an AE
- Any concomitant medications that are taken to treat an SAE
- Any excluded concomitant medications taken as a deviation from the protocol.

Concomitant medications on case report forms will be classified using the WHO Drug Dictionary EnhancedTM (WHO DDE). Frequency and incidence of concomitant medications will be displayed by generic name, sorted by class, and summarized by treatment group, analysis set, and category as defined above. Concomitant medications will be analyzed and presented as follows:

- Concomitant medications taken on the day of and two days after IP administration will be presented separately
- Any psychiatric concomitant medications by period.

8.8.4 Analysis of Suicidal Ideation and Behavior

Suicidal ideation and behavior will be summarized according to suggestions made in the C-SSRS Scoring and Data Analysis Guide [1]. A positive response for suicidal ideation is counted when a participant answers "yes" to any one of the five suicidal ideation questions (Categories 1-5) on the C-SSRS (i.e., a score >0 for suicidal ideation). Serious suicidal ideation is a suicidal ideation score of 4 or 5. A positive response for suicidal behavior occurs when a participant answers "yes" to any one of the five suicidal behavior occurs when a participant answers "yes" to any one of the five suicidal behavior questions (Categories 6-10) on the C-SSRS (i.e., a score >0 for suicidal behavior; the number and percent of positive responses of Positive Ideation, Serious Ideation, and Positive Behavior will be tabulated by treatment group and time period (lifetime, screening, baseline, each Experimental Session (pre- and post-IP), Integrative Sessions, and endpoints). Frequency and incidence of positive or serious ideation and suicidal behavior will be presented using descriptive statistics in tabular format.

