#### **6.3 Safety Measures**

## Columbia Suicide Severity Rating Scale (C-SSRS)

The C-SSRS is a clinician-administered measure of suicidal behavior devised to detect potential suicidal thoughts or behaviors during a clinical trial [75]. It consists of a Lifetime version and a Since Last Visit version that assess suicidal ideation, ideation intensity, and behavior. The C-SSRS consists of a series of questions, and can be administered during a face-to-face interview or over the telephone. The Lifetime version will only be administered at the initial Screening visit. All subsequent administrations will utilize the Since Last Visit version. Participants who are discontinuing medications to participate in the study will complete the C-SSRS before and after medication washout. The C-SSRS Intensity scale for Lifetime obtained a Cronbach's alpha of 0.93 and 0.94 for the Since Last Visit form, and Last Visit C-SSRS severity scores were positively correlated with the BDI "suicide thoughts" item [76].

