**Table 5: Time and Events – Screening and Preparatory Study Procedures** 

			ing Period 6 weeks)		Prep	Preparatory Period w/ Enrollment Confirmation (2 to 11 weeks)							
		Screening	,	Enrollment		ratory	Baseline CAPS-5 T1	Baseline & Enrollment Confirmation					
Visit	Phone Screening	Screening	IR Screening	V0	V1	V2	V3	V4					
Visit Description	Phone Calls	In-person Visits & Labs	Tele- assessment	Enrollment	Prep. 1	Prep. 2	Tele- assessment	Prep. 3 & Enrollment Confirmation					
Visit Timing	Prior to Initial Screening	Over 3 weeks (-2 /+1 weeks)	2 days after initial eligibility met (+7 days)	2 days post IR Screening (+12 days)	Within 1 week of V0 (0 to 12 days)	2 to 21 days of V1	Post V2 & Taper	3 to 6 days after V3; 1 to 4 days before V5					
Initial Phone Screen	√A												
Informed Consent	Send Copy	✓											
Follow-up Phone Screen	√												
Assess Eligibility	✓	√		✓	✓	√		✓					
Medical/Psychiatric History	√ B	✓			√	√		✓					
Past/Current Medication & Adherence	√	√			√	√		√					
Weight, Blood Pressure, Pulse, Temperature		√											
Physical Exam		✓											
ECG C & Rhythm Strip		✓											
Clinical Lab Tests		✓											
Drug Test D		✓						✓					
Pregnancy Test E		✓						✓					
Digital Recording of Visit			√		✓	√	√	✓					
Medication Taper				✓	✓	✓							
Study Enrollment				✓				✓ Confirmed					
AE Assessment F				✓	✓	√		√					
90-min Preparatory Session					✓	✓		✓					
Phone Call Follow-up G						√							

A In Germany phone screening is not permitted

<sup>B At Screening, collect data on previous hospitalizations, healthcare utilization and economic productivity. Request participants to obtain medical/psychiatric records to bring to the next in-person screening visit.

<sup>C ECG to be conducted at any time if clinically indicated.

<sup>D In the UK, also includes testing for alcohol.

<sup>E PABP Only. Urine or serum (UK: serum only).

F Adverse Events (Aes) Assessment includes collecting Serious Adverse Events, Aes of Special Interest, Aes of Psychiatric Status, Aes requiring medical advice or attention, Aes that indicate withdrawal of a participant, and all other Aes

<sup>G If needed, call participant to confirm medication tapering and stabilization is complete prior to Visit 3

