## 13.1.2 Safety Analyses

Safety data will be summarized by exposure to IP, unsolicited AEs, concomitant medications, suicidal ideation and behavior, and vital signs overall. If a participant has more than one AE mapped to the same PT, that AE will be reported once using the highest severity. AEs that occur on Day 0 (Experimental Session), Day 1, Day 2 after IP administration will be presented separately. Report incidence of AEs during Experimental Sessions such as clinical signs and symptoms, such as chest pain, shortness of breath, or neurological symptoms or any other signs or symptoms that may be indicative of a medical complication of the IP.

Frequency and incidence of concomitant medications will be displayed by generic name, sorted by class, and summarized by analysis set and category. Concomitant medications taken on Day 0 (Experimental Session), Day 1, Day 2 after IP administration will be presented separately. Any psychiatric concomitant medications will be tabulated by period (Preparatory, Treatment Period, Follow-up Period). Frequency and incidence of positive or serious ideation and suicidal behavior will be presented using descriptive statistics of C-SSRS scores in tabular format. Vital signs (heart rate, blood pressure, and body temperature) for Experimental Sessions will be summarized using descriptive statistics in tabular format listing values at pre-IP administration, prior to the supplemental dose, and at the end of each Experimental Session. Additional details are available in the Statistical Analysis Plan.

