6.0 Randomization and Blinding

MP18 is an open-label study with no randomization or blinding of treatment.

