8.0 Analyses

Every effort will be made to ensure complete, accurate and timely data collection and to avoid missing data, to ensure the completeness of the data which can impact the integrity and accuracy of the final study analysis. The statistical analyses will be reported using summary tables, figures, and data listings. All analyses and tabulations will be performed using SAS® Version 9.4 or higher, and S-PLUS. In general, nominal variables will be described in terms of frequencies and percentages. Ordinal and non-normal continuous variables will be described using sample median and range.

Approximately normal variables will be described using sample mean and standard deviations and analyzed by parametric statistical tests. Except for the primary effectiveness analysis, all statistical tests will be two-sided and a difference resulting in a p-value of less than or equal to 0.05 will be considered statistically significant. All p-values will be rounded to and displayed in four decimals. If a p-value less than 0.0001 occurs it will be shown in tables as <0.0001. Data not subject to analysis according to this plan will not appear in any tables or graphs, but will be included in the data listings. Selected results may be presented graphically using standard graphical software.

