8.4 Baseline Values

Baseline values are from Baseline Visits for all measures, except C-SSRS, AUDIT, DUDIT, resting blood pressure (BP), Body Mass Index (BMI). For C-SSRS, the initial screening visit will be conducted with the 'Lifetime' version of the measure. The Independent Rater Screening assessment of 'Since Last Visit' suicidal ideation and behavior will be used as 'Baseline.' For the AUDIT and DUDIT measures and resting BP, BMI, results collected at Screening will be used as the Baseline value.

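### The C-SSRS tables in SAP 8.8.4 are by-period counts that cannot show new or worsened ideation within a participant, mainly at scores 1–3, and it is unclear which rows hold V4 and the Day 2 and Day 7 calls

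*SAP*

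**What the plan says.** SAP 8.8.4 defines positive ideation as a yes to any of C-SSRS categories 1–5, serious ideation as a score of 4 or 5, and positive behavior as a yes to any of categories 6–10. It then states that "the number and percent of positive responses of Positive Ideation, Serious Ideation, and Positive Behavior will be tabulated by treatment group and time period". The periods it lists are lifetime, screening, baseline, each Experimental Session before and after IP, Integrative Sessions, and endpoints. It adds that "Frequency and incidence of positive or serious ideation and suicidal behavior will be presented using descriptive statistics in tabular format", and it defers in general terms to an external scoring guide. Protocol 13.1.2 has a similar line: "Frequency and incidence of positive or serious ideation and suicidal behavior will be presented using descriptive statistics of C-SSRS scores in tabular format". On design, SAP 6.0 says "MP18 is an open-label study with no randomization or blinding of treatment".

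SAP 8.4 takes the C-SSRS baseline from the Independent Rater (IR) Screening: that assessment of "suicidal ideation and behavior will be used as" baseline. IR Screening comes before V0, and taper starts at V0. Protocol 6.3 says "Participants who are discontinuing medications to participate in the study will complete the C-SSRS before and after medication washout". The C-SSRS is also given at V4, which Protocol Table 5 places "3 to 6 days after V3; 1 to 4 days before V5" under a column headed as baseline and enrollment confirmation. Footnote C to Protocol Table 7 adds forms at the Day 2 and Day 7 calls after each Experimental Session.

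**The concern.** Without a control arm, a participant's own pre-dose forms are the only reference for worsening. Protocol 9.1.2 names exacerbation of suicidal ideation during and just after psychotherapy sessions as a risk. A table of period totals mixes participants who newly develop ideation with participants whose ideation resolves. It can look flat while both happen.

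The forms that would best support a paired reading are also the ones with unclear places in the table. V4 is the form after taper and before dosing. The Day 2 and Day 7 calls fall in the week when exacerbation is most expected. At stake is whether the report can say how many participants got worse after dosing, in a study meant to support labeling and to inform Phase 3.

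**Working it through.** The plan states no figure on this point, so there is nothing to reproduce. The checks below use the planned maximum of N = 40. All prevalence and correlation values are assumptions, since the documents give none.

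**1. What period counts can show.** Let a participants be positive before dosing and b after. The number of new cases lies between max(0, b − a) and min(b, N − a).

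| Before | After | New cases possible | Maximum as share of those negative before |
|---|---|---|---|
| 4 | 4 | 0–4 | 4/36 = 11% |
| 8 | 8 | 0–8 | 8/32 = 25% |
| 12 | 12 | 0–12 | 12/28 = 43% |
| 16 | 16 | 0–16 | 16/24 = 67% |
| 16 | 10 | 0–10 | 10/24 = 42% |
| 0 | 2 | exactly 2 | 2/40 = 5% |

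With equal counts, new cases equal resolved cases. If 25%, 50% or 75% of 12 pre-dose positives resolve, 3, 6 or 9 of the 12 positives after dosing are new. The last row of the table is the serious-ideation or behavior case: when the pre-dose count is zero, nothing is hidden.

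**2. Worsening within the positive range.** Any yes in categories 1–5 counts once, so a move from 1 to 3 leaves Positive Ideation unchanged and does not reach Serious Ideation.

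**3. Forms and rows.** Before the first dose there are three Since Last Visit forms: IR Screening, V4 and V5 pre-IP. A completer has 14 forms afterwards:
- V5 post-IP, V10 pre-IP and V10 post-IP (3)
- V6, V7, V9, V11, V12 and V13 (6)
- V15 (1)
- Day 2 and Day 7 calls, twice (4)

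If the calls fall under no listed period, 4/14 = 29% of post-dose forms have no row. If they are folded into a listed period, none are lost.

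**4. Look-back.** Reading the form as covering the time since the previous C-SSRS, V4 covers IR Screening to V0 (2–14 days) plus the preparatory period (2–11 weeks). That is 2 + 14 = 16 to 14 + 77 = 91 days. V5 pre-IP covers 1–4 days. On this reading V4 is the form that spans washout. If the form is read as since the last visit of any kind, V4 reaches back only 3–6 days, to V3.

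**5. How a paired table behaves with no true change.** Take each form positive with probability p and within-person correlation r (beta-binomial). The chance of no positive in n forms is Q(n) = product over i = 0 to n−1 of [(1−p)(1−r) + ir] / [(1−r) + ir]. A participant looks newly positive with probability Q(3) − Q(3+m), where m is the number of post-dose forms. Choosing p so that 30% are positive on at least one of the three pre-dose forms gives p = 0.112, 0.150 and 0.199:

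| r | 3 v 14 forms | 3 v 3 forms |
|---|---|---|
| 0 | 57% (about 23 of 40) | 21% (about 8) |
| 0.3 | 27% (about 11) | 11% (about 4) |
| 0.6 | 14% (about 6) | 6% (about 2) |

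At p = 0.02 the figures are 23.2%, 5.9% and 2.2% for 3 v 14, and 5.5%, 2.1% and 0.9% for 3 v 3. Equal form counts do not remove chance switching, but new and resolved cases are then equal in expectation, so an excess of new cases can be interpreted. With 3 v 14 at r = 0 and 30% pre-dose, the resolved share is Q(14) − Q(17) = 18.9% − 13.3%, about 6%, against 57% newly positive.

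**The case against.** The other side has a good case on several points.

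- **AE reporting is participant-level.** Protocol 10.1 counts exacerbation of pre-existing conditions as an AE and asks staff to follow up when a completed measure raises suspicion. SAP 8.8.2 splits AEs into pretreatment, treatment-emergent and follow-up, and counts each participant once per preferred term. This stands as partial cover. It is not complete. The explicit instruction to record increased suicidality as an AE sits under scores of 4 or more in Protocol 9.1.2. SAP 8.8.2 also limits AESIs to cardiac function and abuse liability, although Protocol 10.1.1 includes suicidal ideation.
- **Listings exist.** A reader might infer that untabulated forms vanish, because SAP 8.0 says "Data not subject to analysis according to this plan will not appear in any tables or graphs". The same sentence sends such data to the listings, and with up to 40 participants individual courses could be traced there. A listing is still not a prespecified summary.
- **The calls may already have a row.** Protocol Table 6 and SAP Table 2 tick follow-up calls under V6 and V11, which are Integrative Sessions. The C-SSRS footnote ties them to V5 and V10. Either route leads to a listed period, so the documents do not show that 29% of forms are dropped. They show only that the assignment is not stated.
- **V4 may be the baseline row.** Table 5 labels it so, while SAP 8.4 gives that label to IR Screening. This is a labeling conflict and not a demonstrated omission.
- **The stated objective is largely met.** Safety objective 10 concerns serious ideation and positive behavior, which the exclusions keep near zero at entry.
- **The cited guide cannot be seen here.** It may suggest paired summaries, but the SAP commits to none.

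**Conclusion.** The point holds in a limited form. The C-SSRS summaries that SAP 8.8.4 and Protocol 13.1.2 name are aggregates. In a single-arm study they cannot identify within-participant onset or worsening. At an assumed 12 of 40 before and after, they leave 0 to 12 new cases open. The effect falls mainly on scores 1–3, and the AE tables and listings reduce it without closing it.

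Two stronger readings are not supported. A reader might infer that new serious ideation or behavior would go unseen. With pre-dose counts near zero, those events would show wherever a row exists, although a score of 4 less often than weekly is still admissible at entry. A reader might also infer that the pre-taper baseline is what hides cases. Offsetting arises from the period counts whatever the baseline; the choice of IR Screening matters for separating washout-related change from change after MDMA, and the V5 pre-IP row already gives one aggregate reference after taper and before dosing.

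The conclusion about period counts is arithmetic and needs no assumption. The sizes rest on the assumed prevalences and on the full 40 participants.

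**What to change.** Amend SAP 8.8.4, on the Safety Set:

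1. Keep the by-period table. State that V4 and the Day 2 and Day 7 calls are tabulated, each as its own row, and that percentages are of participants.
2. Add a within-participant shift table of ideation score, with the number and percent who have new or worsened ideation, new serious ideation (4–5) and new behavior. Lead with two equal-form comparisons: V4 to V15; and the worst of the three pre-dose Since Last Visit forms (IR Screening, V4, V5 pre-IP) to the worst of the next-day session, Day 2 and Day 7 forms, separately after each dose (V6 and its calls, V11 and its calls).
3. Show the worst of all 14 post-dose forms against the worst pre-dose form only as a supplementary table, with a printed caution that unequal form counts inflate apparent worsening.

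The cost is SAP wording and a few small tables from forms already collected. The downsides are small cells and the limits of each check. V4 to V15 compares single forms and does not capture the days just after dosing. The 3 v 3 check has a post-dose window of only 7 days against weeks before dosing, so it leans against showing worsening.

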## 7.3.2 Telephone Contact After Experimental Sessions

The goal of the telephone contact is to assess health changes, ensure participant safety, and offer support. The therapy team will follow-up with the participant by telephone on the second and seventh day after each Experimental Session, with two additional telephone contacts in between. Each call will last on average five to 15 minutes but could be longer to address participant concerns and to adequately assess wellbeing. Additional telephone contact can be initiated at the request of the therapy team or participant.

At each telephone contact, the therapy team will:

- Inquire about any possible changes in health, assess the participant's mental health and
  the status of any previously recorded AEs, and record AEs as described in Section 10.0
  Safety
- Inquire about concomitant medication use and compliance
- Offer support in accordance with the Treatment Manual
- On the second and seventh contact day after an Experimental Session the therapy team will administer the Since Last Visit C-SSRS.

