## 9.2.4.1 Common Expected AEs

Common expected AEs were typically observed during Experimental Sessions but were transient and typically diminished as MDMA was metabolized and excreted over the next 72 hours after dosing. In the Phase 3 study MAPP1, the most common adverse events reported more frequently in the MDMA group were muscle tightness, decreased appetite, nausea, hyperhidrosis, feeling cold, restlessness, mydriasis, dizziness (postural), bruxism, nystagmus, increased blood pressure, feeling jittery, chest pain (non-cardiac), dry mouth, vision blurred, pollakiuria, intrusive thoughts, vomiting, stress, and musculoskeletal chest pain. AEs were typically self-limiting.

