## 10.1.1 Adverse Events of Special Interest

The sponsor will pay special attention to a subset of AEs involving psychological distress, including Low Mood (occurring up to 5 days after Experimental Sessions), suicidal ideation and suicidal behavior, as well as cardiac function that could be indicative of QT interval prolongation or cardiac arrhythmias, including Torsade de pointes, sudden death, ventricular extrasystoles, ventricular tachycardia, ventricular fibrillation and flutter, syncope (non-postural), and seizures. These AEs will be marked in the eCRF with the denotation "Adverse Event of Special Interest" (AESIs) whether serious or non-serious.

In order to assess signals of abuse potential for the IP in the intended patient population:

- AESIs involving the terms of Behavioral addiction, Drug abuser, Substance abuser, Dependence, Intentional product misuse (including facilitation of product use outside of research setting), Overdose (accidental, intentional, or prescribed), or Drug diversion will be collected and coded as AESIs in the eCRF if noted in relation to MDMA or Ecstasy.
- Cases of noncompliance, protocol violations, participants lost to follow-up, and any other reasons why participants dropped out of the study will be assessed for presence of AESIs.
- Qualitative urine drug test data will be collected prior to each Experimental Session. Any
  positive findings that cannot be attributed to pre-approved concomitant medications or
  diet will be reviewed by the Medical Monitor to assess compliance with ongoing
  eligibility criteria and for presence of AESIs.

If an AESI is a SAE, it should be reported via the eCRF within 24 hours of the site's awareness of the event.

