¹ All visits must be scheduled to ensure that the Primary Outcome CAPS-5 T3 assessment is within the overall window provided: 13 weeks (+/-3 weeks) post V5

Table 3: Time and Events – Study Measures

	Screening			Baseline Enrollm Confirma	ent tion	Treatment 1				Treatment 2			Follow-up & Study Termination	
	Visit #	Site ^A	IR Screening	IR V3	V4	V5	V6&7	IR V8	V9	V10	V11&12	V13	IR V14	V15
Visit Description	~Time to Complete Measure (minutes)	Site Visit	Tele- assessment	Tele- assessment	Site Visit	Exp. Session 1	Int. Sessions 1.1 & 1.2	CAPS-5 T2: Tele- assessment	Int. Session 1.3	Exp. Session 2	Int. Sessions 2.1 & 2.2	Int. Session 2.3	CAPS-5 T3: Outcome: Tele- assessment	Study Termi- nation
CAPS-5	90 (Baseline) 60 (all others)			\checkmark				\checkmark					\checkmark	
SDS	2			✓				✓					\checkmark	
DSP-I	15			√				✓	1		1		✓	
C-SSRS ^B	10	√	✓		\checkmark	√ ^C	\checkmark		\checkmark	✓ ^C	\checkmark	\checkmark		\checkmark
MINI	15		✓											
CIPD-SR	20	~												
CIPD	60		~											
LEC-5	5	√			✓				\checkmark			\checkmark		\checkmark
PCL-5	8	√			✓				✓			√		✓
DDIS D	5		✓											
ACE	4				✓									
BDI-II	10 (Baseline) 5 (all others)				~									√
CPGS	5				✓									\checkmark
EQ-5D-5L	3				~									✓
SCS	6				~									✓
AUDIT	3	✓												\checkmark
DUDIT	3	✓												\checkmark
SRNU	3				✓									\checkmark
EAT-26	6				✓									\checkmark
UFEC	3				✓									
SE	2					✓				√				
~Total Time o Measures (min		49	105	107	50	12	10	77	23	12	10	23	77	57

 ^A Ensure that LEC-5 and CIPD-SR results are sent to the Independent Rater
^B First C-SSRS is a Lifetime assessment, other assessments are Since Last Visit
^C Conducted pre- and post-IP administration, and at phone calls on Days 2 and 7 after Experimental Session
^D The relevant questions (117 to 132) from the DDIS will be asked by the Independent Rater during the IR Screening visit. The entire measure will never be administered.

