8.8.2 Analysis of Adverse Events

The primary measure of safety will be the reporting of unsolicited AEs. All AEs collected from Enrollment to Termination will be categorized as follows:

- Pretreatment AEs are defined as AEs that occur during the Preparatory Period prior to the first dose in the first Experimental Session
- Treatment Emergent AEs are defined as AEs that occur during the Treatment Period from the first Experimental Session to the last Integrative Session
- AEs that occur on and two days after MDMA or placebo administration
- AESIs are defined as AEs specified in the protocol related to cardiac function and abuse liability
- Follow-up Period AEs are defined as AEs that occur during the Follow-up Period after the last Integrative Session through Termination
- AEs leading to discontinuation of IP
- AEs resulting in death or hospitalization.
- SAEs
- AEs continuing at Termination.

Verbatim terms on case report forms will be mapped to preferred terms (PT) and system organ class (SOC) using the Medical Dictionary for Regulatory Activities (MedDRA) Version 20.0 (Hierarchy), WHO DRUG Enhanced Mar-2018 B3 (Hierarchy and Ingredients).

Frequency and incidence of AEs will be displayed by PT, sorted by SOC, and summarized by treatment group, analysis set, category (as defined above), severity, and seriousness. AEs will be analyzed and presented as follows:

- If a participant has more than one AE mapped to the same PT, that AE will be reported once using the highest severity
- Relationship will be determined based on relative incidence of TEAEs with at least twofold difference between MDMA vs. placebo
- Compare relative incidence of AEs during Experimental Sessions such as clinical signs and symptoms, such as chest pain, shortness of breath, or neurological symptoms or any other signs or symptoms that may be indicative of a medical complication of the investigational product
- AEs that occur on day of Experimental Sessions and two days after IP administration will be presented separately.

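### SAP 8.8.4 names no tabulated period for the C-SSRS forms taken at the Day 2 and Day 7 telephone calls, so lower-level ideation reported in the first week after dosing can be missing from the safety tables

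*SAP*

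**What the plan says.** **Collection.** Protocol 7.3.2 states: "On the second and seventh contact day after an Experimental Session the therapy team will administer the Since Last Visit C-SSRS". Footnote C to SAP Table 3, attached to the Visit 5 and Visit 10 cells, describes the same forms: "Conducted pre- and post-IP administration, and at phone calls on Days 2 and 7 after Experimental Session". Protocol 6.3 says that the Lifetime version is used only at the initial Screening visit and the Since Last Visit version thereafter.

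**Tabulation.** SAP 8.8.4 gives counts and percentages of positive ideation (any score above 0), serious ideation (4 or 5) and positive behavior. The periods are lifetime, screening, baseline, "each Experimental Session (pre- and post-IP), Integrative Sessions, and endpoints". Neither telephone call is named, and the last term in the list is not defined. SAP 8.0 adds a default: "Data not subject to analysis according to this plan will not appear in any tables or graphs". Such data go to listings.

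**Related AESI definition.** Protocol 10.1.1 includes among the AESIs suicidal ideation, suicidal behavior and "Low Mood (occurring up to 5 days after Experimental Sessions" (the parenthesis closes there). The AESI category in SAP 8.8.2 covers only cardiac function and abuse liability.

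**The concern.** The Day 2 and Day 7 calls are the only scheduled C-SSRS contacts between the morning after dosing and the second Integrative Session. Safety objective 10 is the incidence of serious ideation and positive behavior on this instrument, and the overall safety objective is meant to support the package insert. A programmer who follows the list in 8.8.4 literally would build no row for the calls, and the SAP 8.0 default would leave their results in listings.

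At stake is the reported incidence of suicidality in the first week after each dose. The AESI mismatch adds to this: the two psychological events that the protocol singles out, low mood and suicidality, have no AESI category in the SAP through which they would otherwise be shown together.

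**Working it through.** The plan states no figure on this point, so the check compares the schedule with the table list and counts days.

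**1. Scheduled forms with no named row** (SAP Table 3 with footnote C)

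- Per treatment: pre-dose, post-dose, Day 2 call, Day 7 call and three Integrative Sessions = 7.
- Visit 5 to Visit 15: 2 × 7 + 1 (Visit 15) = 15.
- Telephone forms: 2 × 2 = 4, and 4/15 = 27%.
- After dosing, per treatment: 2 of 6 = 33%.
- At the planned maximum of 40 participants, all calls completed: 40 × 4 = 160 forms.

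**2. Do later forms recover the information?**

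Each form is taken to cover the time since the previous one. The first Integrative Session is on Day 1. The second is allowed on Day 3 to 14 (protocol Table 6) and described as approximately two weeks after dosing (protocol Table 1). Let it fall on day k. The days of the interval Day 1 to Day 7 that appear only on a call form are:

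- k after Day 7: 7 − 1 = 6 of 6 days.
- k from 3 to 6: (2 − 1) + (7 − k) = 8 − k.

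| Second Integrative Session | Days reported only at a call, of 6 |
|---|---|
| Day 3 | 5 |
| Day 4 | 4 |
| Day 5 | 3 |
| Day 6 | 2 |
| Day 8 to 14 | 6 |

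On Day 7 itself the result depends on the order: 6 if the call comes first, 1 if the session does.

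**3. Does adverse-event reporting recover it?**

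Protocol 9.1.2 sends a participant into its management plan when the ideation score is 4 or more or behavior is positive, and within that plan increases in suicidality are recorded as AEs. SAP 8.8.4 counts any score above 0 as positive.

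| Finding at a call | Row in the C-SSRS table | Stated route to the AE tables |
|---|---|---|
| Ideation 1 to 3 | none named | none |
| Ideation 4 or 5 | none named | yes |
| Positive behavior | none named | yes |

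**4. Low Mood**

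The only separate post-dose AE display covers the session day and the two days after it. Of the five post-dose days in protocol 10.1.1 it therefore covers Days 1 and 2, which is 2 of 5. Low mood starting on Days 3 to 5 is still tabulated as a TEAE, because that category runs to the last Integrative Session. What is missing is an AESI category and a display over the protocol's window.

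**The case against.** The calls are unnamed, not excluded. Footnote C sits on the Visit 5 and Visit 10 cells, so the calls can be read as part of each Experimental Session entry. The last term in the 8.8.4 list is undefined, the section closes by promising frequency and incidence with no visit restriction, and it defers to an external scoring guide that is not available here. AEs are asked about at every call, and protocol 10.1.1 names suicidal ideation as an AESI with no score threshold, so a site could record a low score as an AE.

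The lenient reading is possible, and this part of the objection stands. But footnote C lists the post-dose form and the telephone calls as separate items, and 8.8.4 carries over only the first. The post-dose form belongs to the end of the session day (protocol Table 8). Pooling it with a Day 7 form would hide the timing that the calls were scheduled to capture. Nothing requires a site to turn a score of 1 to 3 into an AE.

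A reader might go further and infer that adverse events and psychiatric medications after Day 2 are also lost, because the SAP separates "AEs that occur on and two days after MDMA or placebo administration" and "Concomitant medications with a start date of the day of and two days after IP administration". The documents do not support that. Later events stay in the TEAE tables, and later medications in the Treatment Period and psychiatric-medication-by-period tables, so those totals are not understated. The Day 0 to 2 window is also the protocol's own choice (objectives 4 and 8, and section 13.1.2).

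Nor does the protocol's statement that common AEs "typically diminished as MDMA was metabolized and excreted over the next 72 hours after dosing" mark a delayed risk that the window misses. It describes the resolution of events typically seen during the session, which already count on Day 0.

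**Conclusion.** The gap is real and specific: four of 15 scheduled C-SSRS time points have no named row in SAP 8.8.4. Read literally, the plan leaves ideation scored 1 to 3 at a call without a stated route into any safety table. Scores of 4 or 5 and positive behavior at a call would reach the AE tables but not the C-SSRS counts.

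The loss covers 2 to 5 of the 6 days from Day 1 to Day 7 if the second Integrative Session falls on Day 3 to 6, and all 6 if it falls after Day 7. How many participants this would affect cannot be estimated, because the documents give no expected rate of ideation.

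The conclusion rests on two assumptions: that the 8.8.4 list is followed as written, and that a Since Last Visit form looks back to the previous administration, telephone calls included. The documents do not define that reference point. If sites counted back to the last attended visit instead, later forms would recover part of the loss.

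The AESI definitions in SAP 8.8.2 and protocol 10.1.1 disagree on any reading. The point does not extend to a general failure of the AE or medication tables.

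**What to change.** - **SAP 8.8.4:** add telephone contact Day 2 and telephone contact Day 7 after each Experimental Session to the tabulated periods. Add one row per session for any positive response from dosing through Day 7.
- **AESI definition:** reconcile SAP 8.8.2 with protocol 10.1.1. Safety objective 5, in both documents, carries the same narrower wording and should be brought into line.
- **Low Mood:** show Low Mood AESIs over the 5-day window that the protocol already sets.

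The cost is SAP wording and a few table rows. The forms and dates are already collected, so neither visits nor data capture change.
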